4.9.3 Secondary Efficacy Variables

To control the type I error, a sequential testing procedure will be employed with the order of hypothesis defined as in [Section 3.2.2](#) above. All comparisons will be carried out and their result will be interpreted carefully.

Percent change AHI, high-dose arm vs. placebo.

Percent change AHI will be compared between high-dose arm and placebo group using an analysis of covariance (ANCOVA) model with treatment group as factor and baseline AHI (Visit 2) as a covariate. In the ANCOVA model.

Adjusted means, Standard error (SE) of Adjusted means, 95% confidence intervals, within treatment p-values for each treatment group, treatment group difference, 95% confidence interval of the difference and the between-treatment p-values based on the statistical model described above will also be presented

Similar analysis will be carried out for the following treatment comparisons on the percent change AHI score at two-sided 0.05 level of significance.

1. 75/1.5 dose arm vs Placebo arm
2. 25/5 dose arm vs Placebo arm
3. 75/5 dose arm vs. 75/1.5 dose arm
4. 75/5 dose arm vs. 25/5 dose arm
5. 75/1.5 dose arm vs 25/5 dose arm

Proportion of participants with $\geq 50\%$ improvement in AHI, measured in the supine sleeping position, from baseline (Visit 2) to the second PSG visit (Visit 4) in the 75/5 dose group compared with placebo.

Proportion of patients with $\geq 50\%$ improvement in AHI, measured in the supine sleeping position, from baseline to the second PSG visit between 75/5 dose and placebo group will be analyzed using a logistic regression model with the treatment group as factors and baseline AHI Score as a covariate.

Estimate of the odds ratio along with associated 95% Wald confidence interval (CI) and two-sided p-value will be presented

Similar analysis will be carried out for the following treatment comparison on this efficacy variable at two-sided 0.05 level of significance.

1. 75/1.5 dose arm vs Placebo arm
2. 25/5 dose arm vs Placebo arm
3. 75/5 dose arm vs. 75/1.5 dose arm
4. 75/5 dose arm vs. 25/5 dose arm
5. 75/1.5 dose arm vs 25/5 dose arm

Proportion of participants with $\geq 50\%$ improvement in at-home Oxygen desaturation index from baseline (average of 2 baseline nights) to study treatment nights (average of 6 nights) for the 75/5 dose group compared with placebo.

The oxygen desaturation index is the average number of oxygen desaturations 4% or more below the baseline level per hour.

Proportion of patients with $\geq 50\%$ improvement in Oxygen desaturation index from baseline to study treatment nights (average of 6 nights) between 75/5 dose and placebo group will be analyzed using a logistic regression model with the treatment group as factors and baseline Oxygen desaturation index as a covariate.

Estimate of the odds ratio along with associated 95% Wald confidence interval (CI) and two-sided p-value will be presented

Similar analysis will be carried out for the each of following treatment comparison on this efficacy variable

All statistical tests of hypotheses will be two-sided and will employ a level of significance of $\alpha = 0.05$.

1. 75/1.5 dose arm vs Placebo arm
2. 25/5 dose arm vs Placebo arm
3. 75/5 dose arm vs. 75/1.5 dose arm
4. 75/5 dose arm vs. 25/5 dose arm
5. 75/1.5 dose arm vs 25/5 dose arm

Change in the ESS from baseline to the second PSG visit in the 75/5 dose group compared with placebo.

Change from baseline in the ESS at second PSG visit (visit 4) will be compared between 75/5 dose and placebo group using ANCOVA with treatment group as factor and baseline results as a covariate.

Adjusted means, Standard error (SE) of Adjusted means, 95% confidence intervals, within treatment p-values for each treatment group, treatment group difference, 95% confidence interval of the difference and the between-treatment p-values based on the statistical model described above will also be presented

Similar analysis will be carried out for the each of following treatment comparison on this efficacy variable.

All statistical tests of hypotheses will be two-sided and will employ a level of significance of $\alpha = 0.05$.

1. 75/1.5 dose arm vs Placebo arm
2. 25/5 dose arm vs Placebo arm
3. 75/5 dose arm vs. 75/1.5 dose arm
4. 75/5 dose arm vs. 25/5 dose arm
5. 75/1.5 dose arm vs 25/5 dose arm

Change in the PGI-S from baseline to the second PSG visit in the 75/5 dose group compared with placebo.

Change from baseline in the PGI-S at second PSG visit (visit 4) will be compared between 75/5 dose and placebo group using ANCOVA with treatment group as factor and baseline results as a covariate.

Adjusted means, Standard error (SE) of Adjusted means, 95% confidence intervals, within treatment p-values for each treatment group, treatment group difference, 95% confidence interval of the difference and the between-treatment p-values based on the statistical model described above will also be presented

Similar analysis will be carried out for the each of following treatment comparison on this efficacy variable.

All statistical tests of hypotheses will be two-sided and will employ a level of significance of $\alpha = 0.05$.

1. 75/1.5 dose arm vs Placebo arm
2. 25/5 dose arm vs Placebo arm
3. 75/5 dose arm vs. 75/1.5 dose arm
4. 75/5 dose arm vs. 25/5 dose arm
5. 75/1.5 dose arm vs 25/5 dose arm

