8.1.5 Polysomnography

- Methods: Standard overnight PSG recording and data interpretation will be performed in accordance with the American Academy of Sleep Medicine (AASM) scoring manual. Participants will be instrumented with standard PSG electrodes. Time of lights out will be established according to the participants' habitual schedule and kept constant across the PSG study nights. The participants will be given 8 hours of time-in bed.
- Technically Adequate Test: The screening/baseline PSG study must meet the following criteria for participants to enroll:
 - At least 4 hours of sleep.
 - At least 2 electroencephalograms (EEGs) and 2 electrooculography traces for the full night.
 - P nasal for at least 60% of the night and thermistor or both respiratory belts signals for the full night for scoring respiratory events.

- At least 30% of sleep in supine position.

Participants who do not have a technically adequate test at baseline can be retested at the discretion of the investigator.

- Scoring: For uses other than study enrollment, all studies will be scored by centralized PSG technologists, blinded to treatment assignment. Baseline and on-treatment PSGs for each individual participant will be scored by the same technologist. Scoring will be conducted according to the American Academy of Sleep Medicine manual scoring criteria.

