9.4 Primary and Secondary Analyses

The SAP will be developed and finalized prior to database lock. Below is a summary of planned statistical analyses of the primary and secondary endpoints. Further details are presented in the SAP.

Hypothesis tests will be performed in a sequential manner to avoid the need to adjust type I error rates for multiplicity, at a 2-sided 0.05 significance level. The sequential order of hypothesis tests will occur as follows:

- Comparison of the proportion of participants with $\geq 50\%$ improvement in AHI from baseline to the second PSG visit in the 75/5 dose group compared with placebo.
- Percent change AHI, high-dose arm vs. placebo.

- Proportion of participants with $\geq 50\%$ improvement in AHI, measured in the supine sleeping position, from baseline to the second PSG visit in the 75/5 dose group compared with placebo. OSA is often more severe in the supine sleeping position, and variability in time spent in the supine position between baseline and during on-drug PSG tests can otherwise introduce variability.
- Proportion of participants with $\geq 50\%$ improvement in Oxygen desaturation index from baseline (average of 2 baseline nights) to study treatment nights (average of 6 nights) for the 75/5 dose group compared with placebo.
- Change from baseline in the ESS from baseline to the second PSG visit in the 75/5 dose group compared with placebo.
- Change from baseline in the PGI-S from baseline to the second PSG visit in the 75/5 dose group compared with placebo.
- Proportion of participants with $\geq 50\%$ improvement in AHI from baseline to the second PSG visit in the 75/5 dose group compared with the lower treatment dose of 25/5.
- In the case that a statistically significant result for the AHI comparison of dose 75/5 to 25/5 is observed, then the proportion of participants with $\geq 50\%$ improvement in AHI from baseline to the second PSG visit in the 75/5 dose group compared with the lower treatment dose of 75/1.5.

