4.9.1.2 Adjustments for Covariates

Baseline values for all endpoint will be included as a covariate for all efficacy analysis.

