4.9.1.4 Multiple Comparisons/Multiplicity

Hypothesis tests will be performed in a sequential manner to avoid the need to adjust type I error rates for multiplicity, at a 2-sided 0.05 significance level. The sequential order of hypothesis tests will occur as follows:

- Comparison of the proportion of participants with $\geq 50\%$ improvement in AHI from baseline to the second PSG visit in the 75/5 dose group compared with placebo.
- Percent change AHI, high-dose arm vs. placebo.
- Proportion of participants with $\geq 50\%$ improvement in AHI, measured in the supine sleeping position, from baseline to the second PSG visit in the 75/5 dose group compared with placebo.
- Proportion of participants with $\geq 50\%$ improvement in Oxygen desaturation index from baseline (average of 2 baseline nights) to study treatment nights (average of 6 nights) for the 75/5 dose group compared with placebo.
- Change from baseline in the Epworth Sleepiness Scale (ESS) from baseline to the second PSG visit in the 75/5 dose group compared with placebo.
- Change from baseline in the Participant Global Impression of Severity (PGI-S) from baseline to the second PSG visit in the 75/5 dose group compared with placebo.

- Proportion of participants with $\geq 50\%$ improvement in AHI from baseline to the second PSG visit in the 75/5 dose group compared with the lower treatment dose of 25/5.
- In the case that a statistically significant result for the AHI comparison of dose 75/5 to 25/5 is observed, then the proportion of participants with $\geq 50\%$ improvement in AHI from baseline to the second PSG visit in the 75/5 dose group will be compared with the lower treatment dose of 75/1.5.

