4.9.2 Primary Efficacy Variable(s)

Primary efficacy variable is participants with $\geq 50\%$ improvement in AHI score from baseline.

Primary efficacy variable will be summarized by treatment group and visit.

Summaries will include the total number of subjects with assessments, the number of participants with missing measurements, proportion of subjects with $\geq 50\%$ improvement in AHI from baseline and associated 95% confidence intervals.

The primary efficacy endpoint will be analyzed using a logistic regression model with the treatment group as factor and baseline AHI score as a covariate. Estimate of the odds ratio along with associated 95% Wald confidence interval (CI) and two-sided p-value will be presented for primary comparison between 75 mg/5mg dose group and placebo.

Odds ratio estimates, CIs, and p-values will also be presented for other efficacy comparisons under the primary objective:

1. 75/1.5 dose arm vs Placebo arm
2. 25/5 dose arm vs Placebo arm
3. 75/5 dose arm vs. 75/1.5 dose arm

4. 75/5 dose arm vs. 25/5 dose arm
5. 75/1.5 dose arm vs 25/5 dose arm

In the situation of zero events (or < 5 participants) in treatment groups, the logistic model may fail to provide valid parameter estimates. In this situation exact logistic regression (Fisher's exact test) can be used to compare the proportions across treatment groups.

A by-subject listing of the primary efficacy data will be provided.

The primary endpoint analysis will be based on mITT and PP population.

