4.12 Determination of Sample Size

The effect of the drug combination in OSA has been investigated in preliminary academic studies that provide an estimate of effect size in a population similar to the planned Phase 2 study population. Data from a single-night cross-over study showed that a high proportion

of participants, 8/9 (88.9%), with demographic characteristics matched to the planned enrollment criterion of the planned Phase 2 study (baseline AHI ≥ 20 , Body Mass Index [BMI] between 18.5 and 40 kg/m², and age from 25 to 65 years) when treated with a combination of 80 mg atomoxetine and 5 mg oxybutynin achieved a clinically relevant threshold of at least a 50% improvement in AHI score. Using a proposed sample size of n=35 for each of the 4 treatment groups, given 90% power and 2-sided alpha of 0.05, the sample size is powered to detect a difference in proportion of responders between the high-dose group and placebo, assuming a response rate as low as 37% in the high-dose group (compared with the preliminary data that suggests response rate may be as high as 90%) and 5% in the placebo group, estimated based on typical test-retest variability of PSG. Alternatively, if test-retest variability of PSG is higher, resulting in a higher placebo response rate of 10%, the study retains 90% power assuming a response rate in the high-dose group of 46%. Participants that discontinue prior to the second PSG visit will not be replaced and will be considered non-responders.

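### The supine-AHI responder model names baseline AHI, not baseline supine AHI, as covariate, out of line with the SAP's own covariate rule for the third test in the sequence

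*SAP*

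**What the plan says.** SAP 4.9.1.2 sets one general rule: "Baseline values for all endpoint will be included as a covariate for all efficacy analysis". The natural reading is that each endpoint is adjusted for its own baseline.

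SAP 4.9.2 gives the primary model, for overall AHI response, as a "logistic regression model with the treatment group as factor and baseline AHI score as a covariate".

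SAP 4.9.3 gives the supine responder model as a "logistic regression model with the treatment group as factors and baseline AHI Score as a covariate". The outcome in that sentence is AHI in the supine position, but the covariate carries no supine qualifier.

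The next responder model in 4.9.3 is a "logistic regression model with the treatment group as factors and baseline Oxygen desaturation index as a covariate". The ESS and PGI-S models also use their own baselines, and the percent-change model uses Visit 2 AHI, which is its own baseline.

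In SAP 4.9.1.4 the supine comparison stands third, after the primary test and "Percent change AHI, high-dose arm vs. placebo". Five tests follow it: ODI, ESS, PGI-S, 75/5 versus 25/5, and 75/5 versus 75/1.5.

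The protocol treats supine and overall AHI as different quantities. Section 9.4 notes that "OSA is often more severe in the supine sleeping position". Section 8.1.5 requires of the baseline PSG "At least 30% of sleep in supine position".

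**The concern.** A programmer who follows 4.9.3 word for word fits overall baseline AHI. One who follows 4.9.1.2 fits baseline supine AHI. These are two models for one pre-specified test, and near the 0.05 boundary they can disagree. The test is gated: if it fails, no confirmatory claim can be made for the five tests below it, including the only two formal dose comparisons in a dose-finding trial. A choice of this kind should not be open once treatment codes are known.

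There is also a question of efficiency. Baseline supine AHI is the denominator of the supine response, so it is the natural candidate to predict who crosses the 50% line. Overall AHI mixes in non-supine sleep and may predict this less well.

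**Working it through.** **Step 1. Covariates side by side (SAP 4.9.2 and 4.9.3).**

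| Endpoint | Covariate named | Own baseline? |
|---|---|---|
| AHI response (primary) | baseline AHI | yes |
| Percent change in AHI | baseline AHI, Visit 2 | yes |
| Supine AHI response | baseline AHI | not as written |
| ODI response | baseline ODI | yes |
| ESS change | baseline ESS | yes |
| PGI-S change | baseline PGI-S | yes |

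The supine model is the only one out of line, and no reason is given. The same term in the primary model and in the subgroup definition (4.9.1.6) means overall AHI.

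**Step 2. The plan's own power figure.** SAP 4.12 states its sample size "given 90% power and 2-sided alpha of 0.05", with 35 per arm. Summing binomial probabilities over all tables in which the two-sided Fisher exact p is at most 0.05 gives:
- 37% versus 5%: 90.7%
- 46% versus 10%: 90.6%

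The stated figure is reproduced. It concerns the primary endpoint and does not depend on the supine covariate. No power is stated for the supine endpoint.

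**Step 3. Power with each covariate, by simulation.** The model is logit P(response) = a(arm) + g·x, where x is standardized baseline supine AHI. Each a(arm) is set to give the target response rate. Overall AHI is w = ρx + √(1−ρ²)·e, with e an independent standard normal. Each simulated trial of 35 per arm is tested with the Wald test for treatment, once adjusting for x and once for w, with Fisher's test used on separation. The SAP's planning rates are borrowed from the primary endpoint. The odds ratio per SD (exp g), ρ, and the 30% versus 8% setting are assumptions. Differences are power with x minus power with w, in percentage points.

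| Odds ratio per SD | SAP rates, ρ 0.6–0.9 | 30% vs 8%, ρ 0.4–0.9 |
|---|---|---|
| 1.0 | −0.3 to 0.2 | −0.2 to 0.4 |
| 1.5 | −0.1 to 0.3 | 0.0 to 1.5 |
| 2.0 | −0.1 to 0.8 | 1.1 to 2.8 |
| 3.0 | 0.2 to 2.0 | 1.6 to 5.4 |

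The largest gap at the SAP's rates is 97.1% versus 95.1% (46% versus 10%, ρ = 0.6). The largest overall is 69.2% versus 63.8% (30% versus 8%, ρ = 0.4). The SAP-rate runs used 2,500 trials per setting and the others 4,000. Simulation error is about 0.5 to 1 point.

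**Step 4. Different generating models.** Simulating log-normal supine AHI with night-to-night SD 0.35–0.45 gave gains of 1.6 to 4.3 points at correlations of 0.76–0.85 (for example 66.4% to 70.7%, and 89.0% to 90.6%) and nil at 0.93 or above. A further set of 16 settings (night SD 0.3–0.4 on the log scale, correlation 0.81–0.97, 2,000 trials each) gave gains of 0 to 2.4 points. In that set the two models disagreed on significance in 0.1% to 6.0% of trials.

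**Step 5. The small-count fallback.** SAP 4.9.2 allows exact logistic regression, with Fisher's exact test in brackets, when a group has no events or fewer than 5. Assume the supine placebo rate resembles the planning rates. Then P(X ≤ 4) for X ~ Binomial(35, p) is 97% at p = 0.05 and 73% at p = 0.10. If plain Fisher is then used, there is no covariate and the choice has no effect.

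**The case against.** The strongest reply is that 4.9.3 never says overall. The only AHI in that sentence is supine AHI, so the covariate can be read as referring back to it, and 4.9.1.2 supports that reading. This stands as far as it goes: a reader might infer that the SAP has definitely chosen overall AHI, and the text does not prove it. But the same term means overall AHI in 4.9.2 and 4.9.1.6, so the literal reading has at least equal support.

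A reader might also infer that the plan loses power here. The documents give no supine response rates, no correlation between the two baselines and no prognostic strength, so no loss is demonstrated. At the planning rates it is nil to small.

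A third tempting inference is bias or an inflated error rate. Neither follows, because both covariates precede randomization. Overall AHI is also a defensible covariate, since entry is selected on it. What does not stand is leaving it as a silent exception to the SAP's own rule.

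The fallback could make the question moot, but it is permissive and written under the primary endpoint. Its extension to the supine endpoint rests on the general statement in 4.9.1 that other comparisons are tested similarly. Exact logistic regression proper could still carry a covariate.

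Finally, failure at this step closes confirmatory claims only. SAP 4.9.3 says that all comparisons will be run regardless.

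**Conclusion.** The inconsistency is real on a literal reading, and it sits at a gated test, third of eight. It leaves two candidate models that can give different p-values. It does not affect the primary endpoint, the validity of the supine comparison or type I error.

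If overall AHI is used, the power cost is about 0 to 2 points at the SAP's planning rates. It reaches about 5 only when a strongly prognostic supine baseline, a weak correlation and a lower-powered setting are assumed together. It is nil if the supine baseline is not prognostic, or if plain Fisher is applied. All these figures rest on assumed inputs. Severity is minor. Confidence is moderate, because the wording may be loose.

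**What to change.** Before unblinding, change the covariate in the supine responder model of SAP 4.9.3 from baseline AHI score to baseline (Visit 2) supine AHI, which brings it into line with 4.9.1.2.

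The cost is a few words and no new data, since the supine baseline is already needed to define response. One check goes with it. The 30% supine requirement makes the value obtainable for participants enrolled per protocol, but endpoints use the later central reading and SAP 4.9.1.3 allows for missing baselines. The programmer should therefore confirm that no participant drops out of the model for lack of a centrally scored supine baseline.

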4.9.4 Tertiary/Exploratory Variables

Proportion of participants with $\geq 50\%$ AHI decrease and final AHI $< 15/\text{hour}$, PSG nights

Proportion of patients with $\geq 50\%$ AHI decrease and final AHI $< 15/\text{hour}$ between baseline at Visit 4 will be analyzed using a logistic regression model with the treatment group as factors and baseline AHI score as a covariate.

Estimate of the odds ratio along with associated 95% Wald confidence interval (CI) and two-sided p-value will be presented

Similar analysis will be carried out for following treatment comparison

1. 75/1.5 dose arm vs Placebo arm
2. 25/5 dose arm vs Placebo arm
3. 75/5 dose arm vs. 75/1.5 dose arm
4. 75/5 dose arm vs. 25/5 dose arm
5. 75/1.5 dose arm vs 25/5 dose arm

Total sleep time with $SaO_2 < 90\%$, PSG nights

A summary of the number and percentage of subjects who had total sleep time (minutes) with $SaO_2 < 90\%$ during PSG nights will be provided for each treatment group.

Change from baseline in the total sleep time with $SaO_2 < 90\%$ at second PSG visit (visit 4) will be compared between 75/5 dose and placebo group using ANCOVA with treatment group as factor and baseline results as a covariate.

Adjusted means, Standard error (SE) of Adjusted means, 95% confidence intervals, within treatment p-values for each treatment group, treatment group difference, 95% confidence interval of the difference and the between-treatment p-values based on the statistical model described above will also be presented

Similar analysis will be carried out for following treatment comparison

All statistical tests of hypotheses will be two-sided and will employ a level of significance of $\alpha = 0.05$.

1. 75/1.5 dose arm vs Placebo arm
2. 25/5 dose arm vs Placebo arm
3. 75/5 dose arm vs. 75/1.5 dose arm
4. 75/5 dose arm vs. 25/5 dose arm
5. 75/1.5 dose arm vs 25/5 dose arm

Total sleep time with $SaO_2 < 80\%$, PSG nights

Similar analysis will be performed for this endpoint as specified for the endpoint “*Total sleep time with $SaO_2 < 90\%$, PSG nights*”

1. 75/1.5 dose arm vs Placebo arm
2. 25/5 dose arm vs Placebo arm
3. 75/5 dose arm vs. 75/1.5 dose arm
4. 75/5 dose arm vs. 25/5 dose arm
5. 75/1.5 dose arm vs 25/5 dose arm

Snoring index, PSG nights

Snoring index is defined as number of snores per hour of sleep.

Descriptive statistics (n, mean, SD, median, minimum, maximum) for absolute values and changes from baseline of snoring index will be presented by study visits and treatment group.

Change from baseline in the Snoring index at second PSG visit (visit 4) will be compared between 75/5 dose and placebo group using ANCOVA with treatment group as factor and baseline results as a covariate.

Adjusted means, Standard error (SE) of Adjusted means, 95% confidence intervals, within treatment p-values for each treatment group, treatment group difference, 95% confidence

interval of the difference and the between-treatment p-values based on the statistical model described above will also be presented

Similar analysis will be carried out for following treatment comparison

All statistical tests of hypotheses will be two-sided and will employ a level of significance of $\alpha = 0.05$.

1. 75/1.5 dose arm vs Placebo arm
2. 25/5 dose arm vs Placebo arm
3. 75/5 dose arm vs. 75/1.5 dose arm
4. 75/5 dose arm vs. 25/5 dose arm
5. 75/1.5 dose arm vs 25/5 dose arm

Percent of sleep time in the various sleep stages, PSG nights

Descriptive statistics (n, mean, SD, median, minimum, maximum) for absolute values and changes from baseline of percent sleep time in each sleep stages (WASO, Stage N1, Stage N2, Stage N3, Stage REM) will be provided by study visits and treatment group. The percentage of time in each sleep stage will be calculated using two different denominators; 1) amount of time the patient was asleep, 2) total recording time.

Arousal index, PSG nights

Arousal is defined as the total number of all arousals per hour of sleep.

Descriptive statistics (n, mean, SD, median, minimum, maximum) for absolute values and changes from baseline of arousal index will be presented by treatment group.

Change from baseline in the Arousal index at second PSG visit (visit 4) will be compared between 75/5 dose and placebo group using ANCOVA with treatment group as factor and baseline results as a covariate.

Adjusted means, Standard error (SE) of Adjusted means, 95% confidence intervals, within treatment p-values for each treatment group, treatment group difference, 95% confidence interval of the difference and the between-treatment p-values based on the statistical model described above will also be presented

Similar analysis will be carried out for following treatment comparison

All statistical tests of hypotheses will be two-sided and will employ a level of significance of $\alpha = 0.05$.

1. 75/1.5 dose arm vs Placebo arm
2. 25/5 dose arm vs Placebo arm
3. 75/5 dose arm vs. 75/1.5 dose arm
4. 75/5 dose arm vs. 25/5 dose arm
5. 75/1.5 dose arm vs 25/5 dose arm

Oxygen desaturation index, low-dose run in (25/1.5) vs. placebo, or vs 75/5 final dose, at-home nights

The oxygen desaturation index is the average number of oxygen desaturations 4% or more below the baseline level per hour of sleep.

Proportion of patients with $\geq 50\%$ improvement in Oxygen desaturation index will be presented for the following comparisons:

1. Within the 75/5 dose arm, proportion of ODI responders in 75/5 dose period vs proportion of ODI responders 25/1.5 low dose run-in period. The responders in 75/5 dose period will be calculated from average of 2 baseline nights to average of 6 treatment nights and the responders in 25/1.5 dose period will be calculated from average of 2 baseline nights to average of 3 run-in nights.
2. For all 3 active arms combined (i.e. 75/5;75/1.5;25/5) proportion of ODI responders in 25/1.5 low dose run-in period vs proportion of ODI responders in placebo period. The responders will be calculated from average of 2 baseline nights to average of 3 run-in nights and then the comparison will be done between combined active treatments vs placebo.

Estimate of the odds ratio along with associated 95% Wald confidence interval (CI) and two-sided p-value will be presented

All statistical tests of hypotheses will be two-sided and will employ a level of significance of $\alpha = 0.05$.

Proportion of apneas to hypopneas

Proportion of apneas to hypopneas is defined as = $H/(A+H)$.

Where,

A-Number of Apnea with onset during TST

H-Number of Hypopnea with onset during TST

This variable will be derived for each individual subject at both PSG visit (Visit 2 and Visit 4)

Change from baseline in the proportion of apneas to hypopneas at second PSG visit (visit 4) will be compared between 75/5 dose and placebo group using ANCOVA with treatment group as factor and baseline results as a covariate.

Adjusted means, Standard error (SE) of Adjusted means, 95% confidence intervals, within treatment p-values for each treatment group, treatment group difference, 95% confidence interval of the difference and the between-treatment p-values based on the statistical model described above will also be presented

Similar analysis will be carried out for following treatment comparison on this efficacy variable.

All statistical tests of hypotheses will be two-sided and will employ a level of significance of $\alpha = 0.05$.

1. 75/1.5 dose arm vs Placebo arm
2. 25/5 dose arm vs Placebo arm
3. 75/5 dose arm vs. 75/1.5 dose arm
4. 75/5 dose arm vs. 25/5 dose arm
5. 75/1.5 dose arm vs 25/5 dose arm

Correlation of phenotypic traits (Vpassive, Vactive, arousal threshold and Loop gain) with AHI response or subjective outcomes

Sponsor's research team and scientific advisors will perform this exploratory analysis using the PSG data to quantify two key contributors to OSA—pharyngeal collapsibility and compensatory muscle responsiveness—that is applicable to diagnostic polysomnography.

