4.11.3 PSG Parameters

PSG parameters are measured in accordance with the American Academy of Sleep Medicine (AASM) scoring manual (Version 2.4).

Descriptive statistics (n, mean, SD, median, minimum, maximum) for absolute values will be presented for the following PSG parameters by study visits and treatment group. Summary statistics based on change from baseline variable only provided for the key PSG parameter. (details will be provided in the TLFs shell document)

- Periodic limb movements per hour
- Total recording time, Time in Bed, Total Sleep Time, Sleep Onset Latency, REM Latency, Latency to Persistent Sleep, Wake After Persistent Sleep and Sleep Efficiency.
- Spontaneous arousals per hour during sleep, Respiratory arousals per hour of sleep, PLM arousals per hour of sleep, Total number of all arousals per hour.
- Average apnea duration, Central Apneas per hour, Mixed Apneas per hour, Obstructive Apneas per hour, Hypopneas per hour
- Average heart rate during TST, total time in minute that SaO_2 is less than 90% during TST, total time in minute that SaO_2 is less than 80% during TST, minimum oxygen saturation during TST, mean SaO_2 during TST

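### Time with SaO2 below 90% and 80% is tested in raw minutes of sleep, so a Visit 4 difference in sleep time between arms would pass for a difference in oxygenation

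*SAP*

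**What the plan says.** SAP 4.9.4 describes the first endpoint as "A summary of the number and percentage of subjects who had total sleep time (minutes) with" SaO2 below 90% on the polysomnography (PSG) nights. The percentage in that sentence is of subjects, not of sleep time. Change from Visit 2 to Visit 4 is then compared between arms "using ANCOVA with treatment group as factor and baseline results as a covariate". The below-80% endpoint gets the same treatment. The output includes within-treatment p-values as well as between-treatment ones, and for the below-90% endpoint the section adds: "All statistical tests of hypotheses will be two-sided and will employ a level of significance of" 0.05.

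SAP 4.11.3 confirms the unit. Its list includes "Average heart rate during TST, total time in minute that" SaO2 is under 90%, and under 80%, during TST. The general covariate rule in SAP 4.9.1.2 adds nothing about sleep length: "Baseline values for all endpoint will be included as a covariate for all efficacy analysis".

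Other endpoints in SAP 4.9.4 are normalised. Snoring, arousals and the oxygen desaturation index are rates per hour of sleep. For sleep stages, "The percentage of time in each sleep stage will be calculated using two different denominators": time asleep and total recording time.

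Protocol 8.1.5 gives participants 8 hours in bed, with the same lights-out time on both PSG nights. Its adequacy rule, "At least 4 hours of sleep", is stated for the screening/baseline night only. Protocol 8.2 and SAP 4.10.6 name sleep time among the parameters to be monitored by PSG.

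**The concern.** Minutes below a saturation threshold combine two things: the share of sleep spent desaturated and the amount of sleep. Only the first is oxygenation. The ANCOVA adjusts for baseline minutes but has no term for Visit 4 TST, so a treatment effect on sleep time enters the estimate as if it were an effect on oxygen saturation. The plan itself treats sleep time as worth monitoring on treatment, and it compares three active doses that could differ in this respect.

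At stake is the reading of two exploratory endpoints in a study meant to guide dose selection. A dose that shortened sleep could appear to improve oxygenation, a dose that lengthened it could appear to worsen it, and a real worsening could be hidden.

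**Working it through.** **Inputs from the documents.** The unit is minutes during TST (SAP 4.9.4, 4.11.3). The model is change on treatment plus baseline value (SAP 4.9.4). Time in bed is 8 h = 480 min (Protocol 8.1.5). Planned size is 35 per arm (SAP 4.12). The documents give no expected TST, fraction of sleep below threshold, SD or power for these endpoints, so there is no plan figure to reproduce. The TST values and fractions below are assumptions.

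**Identity.** Let M be minutes below threshold, f the fraction of sleep below threshold and T the TST. Then M = f × T. With f unchanged between nights:

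- change in minutes = f × (T at Visit 4 − T at baseline)
- relative change = (T at Visit 4 ÷ T at baseline) − 1, whatever f is
- change in percent of TST = 0, whatever T is

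**Within-person size.** Baseline TST 420 min, no true change in f:

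| Visit 4 TST (min) | Fall in minutes below 90% | f = 5% | f = 10% | f = 20% | f = 30% |
|---|---|---|---|---|---|
| 390 | 7.1% | 1.5 min | 3 min | 6 min | 9 min |
| 360 | 14.3% | 3 min | 6 min | 12 min | 18 min |
| 300 | 28.6% | 6 min | 12 min | 24 min | 36 min |
| 240 | 42.9% | 9 min | 18 min | 36 min | 54 min |

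Example: 0.20 × 420 = 84 min and 0.20 × 300 = 60 min, a fall of 24 min (24/84 = 28.6%).

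**Opposite direction.** If TST rises from 420 to 450 min at f = 10%, minutes go from 42 to 45, an apparent worsening of 3 min (7.1%).

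**Masking.** If TST falls from 420 to 300 min while f rises from 10% to 14%, minutes are 0.10 × 420 = 42 and 0.14 × 300 = 42. A real worsening shows as no change.

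**From person to treatment effect.** With equal baselines and the same f in both arms, the expected between-arm difference in change is f × (Visit 4 TST in one arm − Visit 4 TST in the other). If TST shortens equally in both arms, this is zero. The table's entries are treatment differences only if the comparator arm stays at 420 min.

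**Within-treatment tests.** These have no comparator. If every arm, placebo included, slept 60 min less at f = 10%, each would show a mean fall of 0.10 × 60 = 6 min.

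**Simulation of the SAP's ANCOVA.** 35 per arm, 4,000 runs, no effect on f. Assumed: median f 10% (log-SD 0.8 between and 0.3 within participants), TST 390 min with SD 45, and active-arm Visit 4 TST shorter by the amount shown.

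| TST shorter in active arm by | Mean spurious difference | p < 0.05, minutes | p < 0.05, % of TST |
|---|---|---|---|
| 0 min | 0.0 min | 4.4% | 4.8% |
| 30 min | −4.0 min | 9.3% | 4.6% |
| 60 min | −8.2 min | 22.8% | 4.4% |
| 120 min | −16.6 min | 76.3% | 5.4% |

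The differences exceed 10% of the TST gap because the assumed distribution is skewed: its mean fraction is about 0.10 × exp((0.8² + 0.3²)/2) = 0.144. The first row confirms that with equal TST the test in minutes keeps its level.

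**The case against.** The strongest reply has four parts.

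First, a reader might infer from the 4-hour rule that Visit 4 nights are systematically shorter and that this biases the test. It does not follow. The rule applies identically to all four arms, so it cannot by itself bias a between-arm comparison, and time in bed and lights-out are held the same on both nights. This part stands. What remains is that sleep inside the 8 hours is free to vary by arm.

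Second, a reader might infer a bias in favour of drug. The documents do not support a direction. Protocol 8.2 and SAP 4.10.6 say only that effects on sleep time will be monitored, and the one sleep-related drug effect they name is somnolence. If that lengthened sleep, the bias would run against drug. This also stands.

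Third, minutes is the protocol's own endpoint (total time below each threshold), whereas sleep stages were specified as percentages from the start. The SAP is therefore not departing from the protocol. Percent of TST is also a different quantity, with a post-randomisation denominator. This is a good reason to keep minutes in the report, but not to read minutes alone as oxygenation.

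Fourth, SAP 4.11.3 summarises "Total recording time, Time in Bed, Total Sleep Time, Sleep Onset Latency, REM Latency" and, in the same list, mean and minimum SaO2 during TST, by visit and arm. The ranked sequence also carries an hourly at-home desaturation index. A careful reader could notice an imbalance in TST. The tested estimate and its p-value would still be uncorrected.

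**Conclusion.** The point holds in a limited form. Both SaO2 duration endpoints are tested in a unit that mixes oxygenation with sleep length. A between-arm bias arises only if Visit 4 TST differs by arm, and it then favours the arm that sleeps less. If TST moves alike in all arms, the between-arm test is unbiased, and only the within-treatment p-values are affected.

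On the assumed baseline of 420 min with a constant fraction, a Visit 4 TST of 390 to 240 min lowers minutes by 7% to 43% with no true effect; the treatment effect absorbs only the part that differs by arm. The simulated false-positive rates rest on assumed inputs, and the 120-minute row needs an arm difference that nothing in the documents suggests. The constant fraction is a simplification too: if f itself changes as sleep shortens, percent of TST will also move.

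The endpoints are exploratory and unranked. The primary result, the testing sequence and the sample size do not depend on them. This is a worthwhile refinement, not a threat to the trial's main conclusions.

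**What to change.** In SAP 4.9.4, derive for each PSG night the percent of TST with SaO2 below 90% and below 80% (minutes below threshold ÷ TST × 100). Apply the ANCOVA already planned to the change in each, with the baseline percentage as covariate and the same treatment comparisons. State that conclusions about oxygenation rest on these percentages. Keep the protocol-named minutes variable and report it alongside, with the TST summary by arm from SAP 4.11.3 cross-referenced so that the two can be read together.

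The cost is one extra derived variable and one extra analysis per endpoint, from data already collected. No visit, assessment or sample-size change is needed.
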